4.3 Vulnerable Populations

4.3.1 Inclusion of Women and Minorities: We will enroll eligible patients who give informed consent, regardless of their gender, race, or ethnicity. We expect the study to roughly reflect the racial, ethnic, and gender distribution of the University of Michigan Diabetes Research Registry (DRR)'s patients with diagnosed diabetes. The DRR has over 5,000 registrants, 30% with type 1 diabetes and 70% with type 2 diabetes. There are almost equal proportions of men (49.6%) and women (50.4%), average age is 54.3 ± 15.9 years, and average duration of diabetes is 15.8 ± 11.2 (Mean \pm SD) years. Thirty percent of DRR patients are racial/ethnic minorities. We are oversampling African American and Latino/Hispanic participants by 50%. Every effort will be made to recruit racial and ethnic minority patients and

various genders. We will also recruit participants accessed through the University of Michigan Medical School Office of Research's DataDirect.

4.3.2 Inclusion of Children: This study will focus on adults with a diagnosis of diabetes over the age of 18. Individuals under the age of 18 will be excluded from this study given their financial dependence on an adult. The intervention is designed at the cognitive and developmental and decision-making ability of adults over the age of 18. Children may directly benefit from the intervention through the inclusion of adults, given that the intervention may benefit the household financial situation, therefore an additional intervention exclusive to children may be needlessly redundant.

4.3.3 Economically or Educationally Deprived: As this study population has inclusion criteria of positive report of financial burden or CRN, people with low-income are a key audience for this intervention.

5 PARTICIPANT ENROLLMENT AND RETENTION

5.1 Participant Enrollment

Trained recruitment staff will make initial contact with potential participants via phone or email. Email, address, and telephone lists will be obtained from the University of Michigan Diabetes Research Registry and DataDirect. A study flyer containing study information will also be posted in University of Michigan locations and clinics. Potential participants will be provided with general information about the study and what would be required in order to participate. Participants will be contacted during normal business and early evening hours.

Potential participants who indicate interest in the study will be screened for inclusion/exclusion criteria over the phone. Those participants who are interested in being part of the study and are eligible to participate will be read pertinent parts of the consent form in order to provide them with a thorough understanding of the potential risks and benefits (participants will also go through a full consent process prior to initial data collection). If a potential participant indicates they are interested and are screened eligible but are then difficult to reach, the study team will mail them the study flyer previously mentioned that was posted in UM locations and clinics.

All recruitment and screening will take place in private rooms to ensure participant privacy. Messages left for the participant will not disclose any information about the potential participant. No information about the participant or study will be given to anyone who answers the phone other than the participant. All information with personal identifiers will be stored in either a locked cabinet in a locked office (when paper log books are needed) or on a secured drive on password protected computers.

For patients who are not able to be reached, decline participation, or are ineligible, patient subject identifiers will be destroyed as soon as possible once one of these terminating events occurs. Data will be collected from people who indicate they are not interested in participating in the study (i.e., reason for non-interest, socio-demographics for participants who are eligible and still not interested). We will also collect ineligibility reason for people who are determined to be ineligible to participate in the study. This data will be anonymized with all personal identifiers attached to the information destroyed. The aggregate, anonymized data will be kept for analysis.

5.2 Participant Retention

To further support participant retention the study team will mail participants a series of postcards throughout study participation: thank you postcard, scheduling reminder postcard, happy birthday postcard.

6 STUDY DESIGN AND PROCEDURES

6.1 Experimental Design and Randomization

We will test our hypotheses using a two arm-randomized control trial. In exploratory analyses, we will examine individual differences in response to treatment. We will collect outcome data at 3 time points: baseline, and 6 (-2 weeks/+4 weeks) and 12 months (-2 weeks/+4 weeks) after initial engagement with CareAvenue. Data collectors and analysts will be blind to the study hypotheses, and analysts will be further blinded by which group participants are allocated to.

Participants will be randomized to either usual care or the intervention group receiving CareAvenue. Usual care is defined as existing practices for addressing patients' financial burden and non-medical issues in the clinic flow. We will provide all control group participants with contact information for the Guest Assistance Program (GAP) at the University of Michigan Health System (UMHS). GAP provides assistance with medical and non-medical needs and resources to patients receiving medical care at UMHS. It consists of social workers who work with clients to help them access a variety of resources. Providing contact information for GAP to the control arm will ensure another layer of blinding of the intervention, and provides an opportunity to assess the benefits of an autonomy supportive, multi-component skills-training intervention on outcomes.

6.2 Study Participation

The study duration is five years. The recruitment phase of the study begins in year one and final data collection concludes in year 5. A study timeline can be found in Appendix 1. Individual participant participation will last approximately 1 year from time of enrollment to completion of data collection. See Appendix 2 for a flowchart outlining participant participation requirements throughout the study.

6.3 Overview of the CareAvenue Intervention

CareAvenue, is an interactive website optimized for use on a smartphone or tablet interface. CareAvenue can be completed independently by participants with a variety of computer literacy levels. Our initial pilot work (HUM00097785) demonstrated that no participants, even those with low health literacy, required technical assistance to complete CareAvenue. The PI's current work in low-income, ethnically diverse populations with a low-literacy website intervention embedded with videos also demonstrates that participants require little assistance in navigating website content. Figure 2 shows a flow diagram of CareAvenue. Following an introduction video for CareAvenue, participants will be asked to select aspects of their health and unmet basic needs they find financially burdensome. Additionally, participants will be asked to select resources for which they would like more information on low-cost options. Participants will then watch a video to learn about different care team members and their roles. Then participants will be routed through 5 different categories of resource domains focusing on health and unmet social risk factors in sequential order: 1) medications/supplies, 2) nutrition and food access, 3) diabetes education, 4) health insurance issues, 5) other unmet needs. Figure 2 details the resources. For all resources, we will use an existing, comprehensive resource available

nationwide that connects people to local resources. For each resource, participants will be given instructions on how to navigate the resource on their own. Users will also view videos (in each resource domain) to learn about the different resources and how to communicate with their provider and other health care team members to obtain assistance. After participants review the five domains, they will view a video on practical tips for financial management (see description below). Finally, for each participant, the website will generate an action plan listing the participants' responses, a list of the care team members, a list of the resources for the domains shown in the website, and the financial management topics. Participants will be encouraged to give their provider a copy of the action plan, which will be generated in an easily digestible format to facilitate efficiency in patient-provider communication. CareAvenue will provide options to either print out the action plan to bring to a clinic visit, or request the study team to mail it to the participant or have the study team facilitate the plan being incorporated into their medical health record with HITS support; members of the study team will not access the health record.

6.3.1 Videos: In Year 1, we are developing a series of 8, 1-5 minute videos to embed into CareAvenue. An introduction video will be created to explain what CareAvenue can offer and how to use it. A video will be developed to introduce participants to different care team members. Five videos will be developed to correspond to each of the available solutions guiding participants through the process of navigating communication with their doctor and care team about obtaining resources for selected burdens and learning about the possible benefits of each recommendation. See Appendix 3 for a full breakdown of intervention topics.

A series of focus groups with physicians by the PI⁴⁰ revealed that physicians would like to be able to better utilize the care team to address patient's financial burden and unmet needs. Video modeling can facilitate the learning of new behaviors.⁴¹ The videos will help model for participants how to ask their doctor to obtain a referral or facilitate connection to available professionals within the care team with expertise on addressing specific sources of burden. It will also explain the roles of different health professionals and who is best equipped to assist with specific sources of burden. The last video will describe best practices for household financial management. Best practices will be derived from the Financial Management Behavior Scale (FMBS), a highly reliable measure of financial management, savings and consumer debt (Cronbach alpha=0.81).³⁹ The FMBS was reviewed by financial planners and counselors during development, who verified it has high content and face validity in measuring important financial management behaviors such as staying within a budget or spending plan and saving money from each paycheck.³⁹ The video we develop will illustrate broad tips from the four domains of the FMBS: 1) cash management, 2) savings and investment, 3) credit management/use, and 4) insurance.

The videos will be developed using storytelling methods to communicate key learning points. Storytelling is an effective patient education method for inspiring behavior change and increasing health literacy by simplifying complex ideas while making them actionable in a short period of time.⁴²⁻⁴³ We will use realistic scenarios, case studies, and characters in an active learning, entertaining format to present content. Honey Locust Communications (HLC) (see Support Letter) is developing the videos and making adjustments to the CareAvenue website in partnership with QUICCC NextGen led by [name] (see Resources). HLC will use user-centered design principles.⁴⁴ They will use words, phrases and concepts familiar to the user, rather than system-oriented terms. Only relevant information will appear in a natural and logical order designed in a manner that minimizes the user's memory load.

6.3.2 Follow-up via IVR and text-messaging: Automated IVR and text-message follow-up will be incorporated into the intervention for 1) inquiry around needs being met and appropriate

follow-up (IVR), 2) self-management support (IVR), 3) behavioral reinforcement (text-message), 4) motivation (text-message). These methods have a proven track record for fostering adherence behavior in chronic disease management broadly.²⁹⁻³⁰ We will develop a bank of text messages tailored to intervention content and oriented towards behavioral activation to follow up with resources. Text messages will be sent to participants 3-5 times per week (4-5 times per week for intervention participants and 3-4 times a week for control participants) for 52 weeks. The intervention text messages include content about CareAvenue, whereas the control messages do not. Both intervention and control participants will receive a text message each week asking them to respond with how they rate their diabetes management. A feedback text response will be sent back to participants based on their diabetes management rating. IVR calls allow patients to receive information and respond using their mobile or landline telephone. Additionally, for the intervention participants we will develop IVR messages that inquire about follow-up with resources and ease of access, and automated messages back to the study team if the participant reports needing additional help in navigating resources. IVR calls will be placed on days and times that the intervention participant indicates are convenient, with automatic callbacks in the event that the call is not completed. Each call will take less than 5 minutes to complete, depending on patients' responses. In prior studies, patients have completed more than 80% of weekly IVR assessments over the course of a year.²⁵⁻²⁸ Both IVR and text messaging will be supported by the HIPAA-compliant platform within the University of Michigan Health System.

Pilot Amendments: Amendment 00086864/Amendment 00088719

We will first develop a prototype of CareAvenue refinements and pilot results with a group of 5 participants with type 1 or type 2 diabetes. Participants will be recruited from the UM Health Research Participant Registry and will have varying literacy levels. Participants will be recruited by phone. One-on-one interviews will be conducted with participants at the Ypsilanti District Library. Participants will be asked to complete 3 one-on-one interviews. The 3 interviews will test the CareAvenue prototype for the following:

1. Using the Health-IUEM framework³⁶, we will then assess error prevention, information needs, memorability, learnability, and flexibility/customizability.
2. We will also evaluate the acceptability of the IVR telephone and text messaging administration and content in order to verify the suitability of our content and estimate IVR call length.
3. We will also assess the acceptability of the CareAvenue website in regards to resource content and user experience.

All participants recruited for assessing user-centered design for the refinements of CareAvenue will be given a \$25 MasterCard gift card per interview. Based on their feedback, refinements to CareAvenue will be made.

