related financial burdens and unmet SDHs that impair the ability of adults to effectively manage their chronic conditions. Delivery systems are increasingly pressured to simultaneously implement guideline-recommend care, quality and prevention efforts and behavioral counseling on a growing population of complex patients. New approaches and tools are needed to support complex patients that does not compromise time and resources needed to provide optimal care. Screening for and addressing SDHs must be comprehensive, feasible, evidence-based, and efficient. Activating patients to address health-related financial burden and unmet SDHs is an investment that would maximize the time of both patients and providers, and become generalizable to diverse practice settings. Technology-based approaches represent a promising, scalable approach to screen for SDHs, provide information on locally available resources to meet identified needs, and prompt patients to seek out resources, share information efficiently with their providers, and make behavior changes that can improve health status.²² Communication technologies such as smartphones and tablets that provide internet access are increasingly available to patients across the spectrum of socioeconomic status.²³⁻²⁴ Text-messaging and interactive voice response (IVR) methods are effective in improving patient monitoring, self-care behaviors, adherence, and in turn disease control.²⁵⁻³⁰ They can also be integrated into health systems given the universal adoption of electronic health records. We reviewed >100 chronic disease and financial management/literacy mobile apps available on the market. We found that none link individuals to low-cost resources that comprehensively address health-related financial burden and SDHs, while also providing skills training and feedback in navigating complex healthcare and community resource infrastructures, and attending to other determinants of meeting disease management goals.

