2 OBJECTIVES

The overall objective is to determine the extent to which activating patients to address health-related financial burdens that impact treatment adherence and unmet SDHs improves disease control, and the mechanisms through which primary and secondary outcomes are achieved. The specific aims of the study are listed below.

Aim 1: Determine the effectiveness of CareAvenue relative to usual care in improving glycemic control and patient-centered outcomes such as CRN behaviors and perceived financial burdens. We hypothesize that participants randomized to CareAvenue will have a change in HbA1c (**primary outcome**) compared to usual care. We will measure the change in HbA1c at baseline, 6 months (-2 weeks/+4 weeks), and 12 months (-2 weeks/+4 weeks) using an HbA1c machine. Additionally, we hypothesize that other patient-centered outcomes (**secondary outcomes**) will change compared to usual care. Secondary outcomes will be measured at baseline, 6 months (-2 weeks/+4 weeks), and 12 months (-2 weeks/+4 weeks). They include blood pressure (measured with an automated blood pressure cuff), Cost-related non-adherence behaviors with prescribed treatment regimens related to diabetes, Cost-related non-adherence behaviors with prescribed treatment regimens related to other conditions being managed, Perceived financial burden, and unmet social risk factors.

Aim 2: Examine mediators and moderators of the effectiveness of CareAvenue on primary and secondary outcomes. We hypothesize that the intervention will significantly improve skills and self-efficacy in uptake and use of resources leading to decreased financial burdens, perceived stress of unmet SDHs, and improved adherence to treatment regimens, with these changes being the primary mechanism through which improvements in glycemic control are achieved. We also hypothesize that CareAvenue will be most effective among patients with high need for resources and low self-efficacy in navigating resources at baseline.

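### Aim 1 claims an effect relative to usual care, but controls receive a year of study texts, weekly rating feedback and GAP contact information, so the trial estimates an added effect over enhanced usual care

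*Combined protocol and SAP*

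**What the plan says.** Section 2 states Aim 1 as: "Determine the effectiveness of CareAvenue relative to usual care in improving glycemic control". Section 6.1 defines the comparator: "Usual care is defined as existing practices for addressing patients' financial burden and non-medical issues in the clinic flow". The same paragraph says the study will give every control contact details for GAP, an existing social-work service of the health system. It offers two reasons. One is masking: "Providing contact information for GAP to the control arm will ensure another layer of blinding of the intervention". The other is the chance to assess a skills-training package with several parts.

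Section 6.3.2 then sets the text schedule: "4-5 times per week for intervention participants and 3-4 times a week for control participants) for 52 weeks". It adds: "Both intervention and control participants will receive a text message each week asking them to respond with how they rate their diabetes management", and "A feedback text response will be sent back to participants based on their diabetes management rating". The one stated difference in content is that control texts carry nothing about CareAvenue. The Data and Safety Monitoring Plan (DSMP), Section II.A, confirms this by listing texts under both groups and GAP services under the control group.

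The protocol regards this mode of contact as active. Section 1.1 says: "Text-messaging and interactive voice response (IVR) methods are effective in improving patient monitoring, self-care behaviors, adherence, and in turn disease control". Section 6.3.2 lists text follow-up among the intervention's own components, for behavioural reinforcement and motivation.

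Section 10, repeated in DSMP Section III.A, plans to read pre/post change in controls as a measure of how far they gained from better provider communication without the e-health tool. It says this will show an effect across the whole practice.

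**The concern.** The definition of usual care does not mention the texts, the rating or the reply, and nothing in the documents presents them as routine care. The comparator in the stated aim and the comparator delivered are therefore different.

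Two conclusions depend on this. First, if the study texts or the GAP contact help controls, the arms move closer together. A small or null difference could then be reported as no benefit over usual care when the trial never observed usual care. Second, the spillover reading in Section 10 needs controls to have received nothing from the study that could move their outcomes. They receive three things that might. The GAP contact also bears on secondary outcomes, because its social workers help people reach resources, and perceived financial burden and unmet social risk factors are both measured.

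**Working it through.** **1. Contents of each arm (Sections 6.1, 6.3, 6.3.2; DSMP Section II.A)**

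| Component | Intervention | Control | In the Section 6.1 definition of usual care? |
|---|---|---|---|
| CareAvenue website and action plan | yes | no | no |
| Interactive voice response (IVR) calls | yes | no | no |
| Texts with CareAvenue content | yes | no | no |
| Study texts, any content | 4–5 a week | 3–4 a week | no |
| Weekly self-rating with a reply | yes | yes | no |
| GAP contact details supplied by the study | not stated | yes | added after the definition; the service itself already exists |

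No arm receives existing practice alone.

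**2. Amount of study contact in the control arm**

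- Control: 3 × 52 = 156 to 4 × 52 = 208 texts.
- Intervention: 4 × 52 = 208 to 5 × 52 = 260 texts.
- Ratio at matching ends: 156/208 = 75% and 208/260 = 80%.
- Rating prompts: 1 × 52 = 52 in each arm. The text does not say whether these fall within the weekly totals.

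These are counts of messages with different content. They show that control contact is substantial. They do not measure a shared effect on HbA1c.

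**3. What the contrast identifies**

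Let I be the mean HbA1c change under the intervention, C the change under the control arm as delivered, and U the change under existing practice. Then:

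I − U = (I − C) + (C − U)

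Randomisation gives an unbiased estimate of I − C. Aim 1 names I − U. The two agree only if C − U = 0, and the trial has no data on U. Every control gets the additions, so there is no untreated subset from which to estimate C − U.

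**4. What the sample size allows for**

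Section 10 starts from 510 with outcome data, adds 3% for physician spillover and allows 12% loss: 510 × 1.03 = 525.3, and 525.3 / 0.88 = 597, consistent with the planned 600. The only dilution named is physician spillover. If 0.53 is meant as the difference against the comparator delivered, no further allowance is needed. If it is meant against existing practice, the texts and GAP contact are not covered. Section 10 does not say which.

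**5. The spillover reading**

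Pre/post change in controls combines any provider spillover with any effect of the texts, the feedback and the GAP contact. Comparing within providers, as Section 10 proposes, does not separate them, because every provider's control patients receive the same additions.

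**The case against.** The strongest reply is that this is a sound, disclosed attention control with an imprecise label. Much of that stands. The GAP contact is stated in the paragraph that defines usual care, with reasons, and it points to an existing service; only contact details are handed over. The text schedule is open in Section 6.3.2. Matching contact across arms so that its non-specific effects cancel is a recognised design. The usual-care definition concerns financial burden and non-medical issues, while the weekly prompt concerns diabetes management. The protocol's statements on effectiveness cover texting and IVR together, and control-text content is otherwise undescribed, so how active the texts are is unknown. If the additions help controls, or do nothing, a positive result is conservative against usual care.

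None of this reconciles Aim 1 with Section 6.3.2. The primary outcome is HbA1c, and a weekly diabetes-management rating with a reply is aimed at self-care, whatever the scope of the definition. Disclosing GAP does not cover the texts. The participation flowchart is not shown in the text available and might describe the control arm more fully, but it would not alter the wording of Aim 1.

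A reader might infer more: that the comparison is biased, that the trial is underpowered, or that a known share of the effect is lost. The documents support none of these. The contrast is valid for the comparator delivered. No figure is given for the effect of the control texts or GAP contact. Section 10 also says its design figures come from early data in the study; if those data include texted controls, any dilution may already be in the 0.53.

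**Conclusion.** Wrong as written, in the naming of the comparator and in what is to be concluded from it. The trial estimates the added effect of the CareAvenue website, action plan, IVR calls and CareAvenue-specific texts over enhanced usual care. It does not estimate the effect over existing practice. A null or small difference would not show lack of benefit over usual care, and control-arm change cannot be attributed to provider spillover.

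The size can be stated only as exposure: 156 to 208 texts and 52 rating prompts per control over the year, plus the GAP contact. The shift in HbA1c cannot be derived from the documents. Attenuation is the likely direction, on the assumption that the additions help and do no harm. The conclusion about what is estimated does not need that assumption; it needs only that the texts and feedback are not already part of existing practice, and no section says they are.

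**What to change.** - In Aim 1 and Section 6.1, name the comparator *enhanced usual care (text messages without CareAvenue content, weekly rating with feedback, GAP contact information)*.
- Word the Aim 1 hypothesis and the primary conclusion as the added effect of CareAvenue over that comparator, and state that a null result does not show lack of benefit over existing practice.
- In Section 10 and its repeat in DSMP Section III.A, remove or qualify the statement that control-arm change quantifies provider spillover and demonstrates a practice-wide effect.
- Report control-arm replies to the weekly text beside the primary result, from the SMS data that Section 7.3 says are stored. Section 7.2 currently measures engagement only by IVR calls and web analytics.
- Report GAP use only if the Section 6.4 survey item on resources in current use captures it. The survey is not in the documents, so the sponsor should check this first.

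The design, the control contact and the sample size can stay as they are. The cost is protocol wording, one descriptive table from stored data and possibly a second. The downside is a narrower headline claim.
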